1.0 Objectives / Specific Aims

In this study, our main goal is to establish transcutaneous auricular vagus nerve stimulation (taVNS) as an effective non-invasive neuromodulation method for analgesia of post-stroke upper extremity pain.

We will recruit up to 20 participants with chronic post-stroke upper extremity pain from the greater Charleston area using MUSC COBRE resources. Participants are required to have an ischemic or hemorrhagic stroke that occurred at least 6 months prior and are currently suffering upper extremity pain. Each participant will undergo an in-person visit to our lab at MUSC [name]. They will first finish the pain questionnaires and have quantitative sensory testing (QST) conducted to determine baseline pain thresholds. Participants will then receive 30 minutes of taVNS (either active or sham). Upon the completion of the stimulation intervention, they will then be tested for another QST and pain questionnaires. All research is being done at MUSC [name] Center for Biomedical Imaging.

Aim 1: Test the safety and feasibility of taVNS in participants with chronic post-stroke upper extremity pain.

Over the last 8 years, our group has demonstrated that taVNS is safe and feasible in several different populations in our previous studies. Specifically, we have demonstrated that taVNS is well tolerated and safe for participants with chronic stroke in our previous clinical trial ([name] et al., 2023, [name] et al., 2023). In this study, we will further verify the safety and feasibility of taVNS in the population with chronic post-stroke upper extremity pain.

Aim 2: Investigate whether taVNS can modulate pain in this population compared to sham.

In this single-visit, single-blinded, sham-controlled pilot trial, we will compare changes in post-stroke upper extremity pain scores and pain threshold derived from QST before and after a 30-minute taVNS intervention, as well as between active and sham taVNS. The findings will help us understand whether taVNS can modulate pain in this population.

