3.0 Intervention to be studied (if applicable)

The intervention we are studying is transcutaneous auricular vagus nerve stimulation (taVNS) which is simply electrical nerve stimulation administered at the ear which targets the auricular branch of the vagus nerve. In this study, taVNS will be administered using the Spark Sparrow Ascent System which is a non-significant risk

investigational device. The Spark Sparrow Ascent System is based on an FDA-cleared device provided by Spark Biomedical and has completed all safety and compliance testing. taVNS is a non-significant risk method that has been approved by the MUSC IRB for many ongoing taVNS trials. [name] are the PI or Co-I of more than seven ongoing taVNS trials. The Spark device summary has been uploaded to the MUSC IRB portal.

In this study, we will use the device as an anti-pain device in participants with chronic post-stroke upper extremity pain. Participants will be randomized to receive 30-minute active taVNS (tragus and cymba conchae) or sham taVNS (earlobe) during their in-person visit. In prior studies in our laboratory, we demonstrated that taVNS can be safely and feasibly administered in chronic stroke populations ([name] et al., 2023, [name] et al., 2023).

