4.0 Study Endpoints (if applicable)

Primary Outcome: *Safety and Feasibility*

The main outcomes of this pilot trial will be the safety and feasibility of implementing taVNS in the population with chronic post-stroke upper extremity pain.

Secondary Outcomes: *Quantitative Sensory Testing (QST)*

We will systematically determine information about A β (sensory), A δ (pain), and C (pain tolerance) fiber activity with a 30 \times 30 mm thermode attached to the non-affected forearm (left arm) of participants (TSA2 thermode; Medoc, Durham, NC, USA). Using the TSA2, we will determine heat sensory, pain, and tolerance thresholds using the method of limits, beginning at 32°C and increasing by 0.5°C per second. Participants will be asked to press a button (to record temperatures) when the stimulus is first detected (sensory threshold), when it becomes painful (pain threshold), and then when the stimulus is intolerable (pain tolerance). When ‘intolerable’ is indicated, the thermode ceases heating and quickly returns to 32°C. This is repeated for 5 trials to obtain average sensory, pain, and tolerance thresholds. We will acquire QST data before and after the 30-minute taVNS. We will explore the analgesic effects by comparing the pre- and post-intervention QST ratings.

Secondary Outcomes: *Subjective Pain Ratings*

Participants will rate their post-stroke upper extremity pain intensity before and after the taVNS using a standard numeric pain rating scale (0-10). We anticipate participants will rate lower pain intensity post-intervention.

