6.0 Number of Subjects

We will recruit 20 participants with chronic post-stroke upper extremity pain for this study.

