channels of stimulation (auricular vagus, auricular trigeminal, and both). Two individual stimulation frequencies will be set: 15 Hz at cymba concha and 100 Hz adjacently anterior to tragus. The pulse duration will be set to 250 μ s for all participants. The stimulation intensities delivered (in mA) will be a standardized 2X Perceptual Threshold. This means that all individuals will first have a perceptual threshold conducted, during which incremental increases and decreases in current intensity will be applied until the participant barely feels the stimulation. That is considered the perceptual threshold. All stimulation then will be delivered at 2X this value. Perceptual threshold will be conducted at the beginning of the taVNS intervention. This is how we have conducted stimulation at MUSC in prior IRB-approved studies which have been safe and rated comfortable and not painful. Sham stimulation will be administered at identical parameters of cymba concha, however, the electrodes will be attached to the earlobe, which is not believed to have a high density of cranial nerve innervation. If the participant states that the stimulation intensity is discomforting or imperceivable in any of the stimulation groups, the researcher will gradually decrease until a comfortable stimulation intensity is achieved. The taVNS session will last for 30 minutes.

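### The main goal in Section 1.0, to establish taVNS as an effective analgesic, exceeds what a single-session pilot of up to 20 people with a safety and feasibility primary outcome can show

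*Protocol*

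**What the plan says.** Section 1.0 opens with an efficacy goal: "our main goal is to establish transcutaneous auricular vagus nerve stimulation (taVNS) as an effective non-invasive neuromodulation method for analgesia". The sentence is tied to the present study, not to a wider research programme.

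The rest of the protocol is more cautious:

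- **Aims (Section 1.0).** Aim 1 tests safety and feasibility. Aim 2 only investigates whether taVNS modulates pain relative to sham, by comparing changes from before to after stimulation. It is introduced with "In this single-visit, single-blinded, sham-controlled pilot trial".
- **Endpoints (Section 4.0).** "The main outcomes of this pilot trial will be the safety and feasibility" of taVNS in this population. Quantitative sensory testing (QST) and the 0-10 pain rating are both secondary, and the QST comparison is described as exploratory.
- **Size.** Section 1.0 says "We will recruit up to 20 participants with chronic post-stroke upper extremity pain"; Section 6.0 says "We will recruit 20 participants with chronic post-stroke upper extremity pain for this study". Neither gives a derivation.
- **Allocation (Section 3.0).** Participants are randomized to active or sham stimulation, with no ratio stated.
- **Exposure (Section 10.0).** There is one session: "The taVNS session will last for 30 minutes". Pain is measured before and after it, with no later follow-up.

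**The concern.** The stated main goal and the stated main outcome answer different questions. The goal is confirmatory and concerns analgesia; the primary outcome is safety and feasibility. No primary outcome serves the goal as written.

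The objective is the natural yardstick for the results. Against the current sentence, a non-significant pain comparison could be read as failure even though the trial has little power for moderate effects. A nominally significant one could be read as efficacy established, from one session in about 20 people on a secondary outcome.

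**Working it through.** **1. The statements side by side.**

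| Place | What it commits the study to |
|---|---|
| Section 1.0, main goal | Establish effectiveness for analgesia |
| Section 1.0, Aim 1 | Test safety and feasibility |
| Section 1.0, Aim 2 | Investigate whether pain is modulated, active versus sham |
| Section 4.0, primary | Safety and feasibility |
| Section 4.0, secondary | QST thresholds (exploratory) and 0-10 pain rating |

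Only the first row is confirmatory. This mismatch needs no arithmetic.

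**2. Inputs for the size of the gap.** From the protocol: 20 participants in total, two arms, and pain measured once before and once after the session. Assumed, because the protocol gives none of them: 1:1 allocation (10 per arm), a two-sided 5% test, no dropout, equal SD in both arms and at both times, and a pre-post correlation ρ of 0.5 or 0.7. Differences are in units of the SD of the raw score. There is no stated power calculation to reproduce.

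**3. 95% CI half-width for active minus sham.**

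- Unadjusted post score: t(0.975, 18) × √(2/10) = 2.101 × 0.447 = **0.94 SD**.
- Change scores, as Aim 2 now plans: 2.101 × √(0.2 × 2(1 − ρ)). At ρ = 0.5 this is 2.101 × 0.447 = **0.94 SD**; at ρ = 0.7, 2.101 × 0.346 = **0.73 SD**.
- Post score adjusted for baseline: t(0.975, 17) × √(0.2 × (1 − ρ²)). At ρ = 0.5 this is 2.110 × 0.387 = **0.82 SD**; at ρ = 0.7, 2.110 × 0.319 = **0.67 SD**.

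The adjusted analysis is narrower than change scores at both correlations and uses the same data.

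**4. Power (noncentral t).**

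| True difference | Unadjusted | Adjusted, ρ = 0.5 | Adjusted, ρ = 0.7 |
|---|---|---|---|
| 0.5 SD | 18.5% | 23% | 32% |
| 0.8 SD | 39.5% | 50% | 66% |
| 1.0 SD | 56% | 68% | 84% |

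The difference detectable with 80% power is 1.32 SD unadjusted and 1.15 SD adjusted at ρ = 0.5.

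**5. On the 0-10 scale.** If the raw-score SD were 2 points (an assumption), the half-widths at ρ = 0.5 would be 0.94 × 2 = 1.9 points unadjusted and 0.82 × 2 = 1.6 points adjusted. At ρ = 0.7 the adjusted half-width would be 0.67 × 2 = 1.3 points.

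**The case against.** The best reply is that one introductory verb is at issue. Aims 1 and 2 are already modest, the study is called a pilot, pain is ranked secondary, and no success criterion or decision rule hangs on the goal sentence. That is largely right, and it limits the consequence: the endpoint hierarchy is sound and a small pilot is not a fault. It does not remove the mismatch, because the sentence speaks of this study and calls efficacy its main goal.

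A reader might go further and infer that the trial would miss most real effects, or that only exaggerated estimates could reach significance. The protocol does not support either as a general statement. It gives no expected effect. Unadjusted power passes 50% at about 0.93 SD, and the smallest observed difference that reaches significance is 0.94 SD, so both claims hold only if the true effect is below roughly 0.9 SD. With baseline adjustment that boundary is lower still, about 0.8 SD at ρ = 0.5. A very large effect could be detected.

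It can also be said that the analysis model belongs in a statistical analysis plan, which may exist. An absent model would indeed be no finding. But Aim 2 already names a comparison of changes, so improving that stated comparison is fair comment.

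**Conclusion.** The point holds as an overstated objective. Section 1.0 sets a confirmatory efficacy goal that conflicts with its own aims and with Section 4.0. The conclusion rests mainly on the text: pilot status, a safety and feasibility primary outcome, pain as secondary, and one session without follow-up.

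The figures are illustrative. With 10 per arm, the interval for active minus sham runs about 0.67 to 0.94 SD either side of the estimate, depending on adjustment and correlation. Power at 0.5 SD is about 19% unadjusted and 23% adjusted at ρ = 0.5, and stays near 32% at ρ = 0.7. Moderate effects could therefore be neither reliably confirmed nor excluded. Because 20 is described in Section 1.0 as an upper limit, actual precision could be lower.

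**What to change.** In Section 1.0, restate the main goal as assessing the safety and feasibility of taVNS in this population and obtaining a preliminary estimate of the active-versus-sham difference in pain.

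In Aim 2, replace the comparison of changes with the active-minus-sham difference in the post-stimulation score, adjusted for the baseline score already collected. Report it with a 95% confidence interval and describe it as preliminary, not confirmatory. If a statistical analysis plan exists, align it.

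The cost is a more modest stated claim, one changed analysis and one degree of freedom for the baseline term. Under the assumptions above, the half-width falls from 0.94 to 0.82 SD at ρ = 0.5, and from 0.73 to 0.67 SD at ρ = 0.7, compared with change scores. No extra patients, visits or measurements are needed.

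### Aim 2 words the active-versus-sham comparison of the secondary pain outcomes as a comparison of changes, without mentioning adjustment for the baseline that is already measured

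*Protocol*

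**What the plan says.** The between-arm comparison of pain is stated once, in Aim 2 (Protocol, section 1.0): "we will compare changes in post-stroke upper extremity pain scores and pain threshold derived from QST before and after a 30-minute taVNS intervention", followed by "as well as between active and sham taVNS". The quantity named is change.

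Section 4.0 makes pain secondary. The primary outcome is safety and feasibility ("The main outcomes of this pilot trial will be the safety and feasibility of implementing taVNS"). For QST the section says "We will acquire QST data before and after the 30-minute taVNS" and "We will explore the analgesic effects by comparing the pre- and post-intervention QST ratings", with no model and no mention of the arms. The 0-10 pain rating is also taken before and after stimulation. Each Aim 2 pain measure therefore has its own baseline.

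On design, section 3.0 says "Participants will be randomized to receive 30-minute active taVNS (tragus and cymba conchae) or sham taVNS (earlobe) during their in-person visit" and section 6.0 says "We will recruit 20 participants with chronic post-stroke upper extremity pain for this study" (section 1.0 says up to 20). The protocol states no allocation ratio, SD, pre-post correlation, effect size, alpha or power. Baseline adjustment is neither planned nor excluded. The SAP is not among the documents at hand.

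**The concern.** Comparing raw changes between arms treats the post-stimulation value as if it rose one unit for each unit of baseline. When the pre-post correlation is below 1 (and the SDs are equal), the true slope is smaller and subtraction over-corrects. The arm that happens to start higher then shows the larger fall without any treatment effect. On the pain rating, where a fall is the benefit, this flatters the arm that starts with more pain. On a QST threshold, where a rise is the benefit, it penalises the arm that starts higher.

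In a trial of 20, chance baseline differences of noticeable size are common. Section 1.0 gives the main goal as establishing taVNS as effective for analgesia, and Aim 2 is the only aim that speaks to it. The active-sham estimate will therefore be read closely although it is secondary. If the model is left open, the choice between an adjusted and an unadjusted analysis could also be made after the data are seen.

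**Working it through.** The protocol gives no power or precision figure, so there is nothing to reproduce. The check compares the two analyses that the wording allows.

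**Inputs**
- From the protocol: N = 20 (section 6.0); two randomized arms (section 3.0); a pre and a post value for each pain measure (section 4.0).
- Assumed: 1:1 allocation, so n = 10 per arm; equal pre and post SD, with results in units of that SD; normal outcomes; two-sided alpha 0.05; rho varied from 0.3 to 0.95.

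**Step 1: size of chance imbalance.** The SD of the baseline difference between arms is sqrt(2/n) = sqrt(2/10) = 0.447. The difference exceeds 0.5 SD in either direction with probability 2 x [1 - Phi(0.5/0.447)] = 0.26.

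**Step 2: effect on the change score.** Given a baseline difference D (active minus sham), the expected error is (rho - 1) x D. Averaged over all randomizations D has mean zero, so the error averages to zero.

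**Step 3: variances**
- Change score: 2(1 - rho)(2/n).
- ANCOVA, averaged over the random imbalance: (1 - rho^2)(2/n)(1 + 1/(2n - 4)). The last factor is 1 + 1/16 = 1.0625, the price of estimating the slope.
- Ratio, ANCOVA to change score: 1.0625 x (1 + rho)/2.

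Example at rho 0.5: 2 x 0.5 x 0.2 = 0.200 against 0.75 x 0.2 x 1.0625 = 0.159, a ratio of 0.80.

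| rho | Change-score variance | ANCOVA variance | Ratio | Change-score error if D = 0.447 SD | Detectable difference at 80% power, change vs ANCOVA (SD) |
|---|---|---|---|---|---|
| 0.3 | 0.280 | 0.193 | 0.69 | -0.31 | 1.57 vs 1.31 |
| 0.5 | 0.200 | 0.159 | 0.80 | -0.22 | 1.33 vs 1.19 |
| 0.7 | 0.120 | 0.108 | 0.90 | -0.13 | 1.03 vs 0.98 |
| 0.8 | 0.080 | 0.077 | 0.96 | -0.09 | 0.84 vs 0.82 |
| 0.9 | 0.040 | 0.040 | 1.01 | -0.04 | 0.593 vs 0.597 |
| 0.95 | 0.020 | 0.021 | 1.04 | -0.02 | 0.419 vs 0.428 |

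Detectable differences use the noncentral t distribution with 18 df (change) and 17 df (ANCOVA). The variances are equal at rho = 2/1.0625 - 1 = 0.88. Counting the lost degree of freedom (critical t 2.110 against 2.101), break-even is about 0.87.

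**Step 4: simulation.** There were 200,000 trials at each of rho 0.5, 0.7, 0.8 and 0.9.
- Both methods averaged 0.80 for a true effect of 0.80 SD, and both rejected about 5% of the time under no effect.
- Power for 0.80 SD, change vs ANCOVA: 39% vs 47% (rho 0.5), 59% vs 63% (0.7), 76% vs 78% (0.8), 96.5% vs 96.2% (0.9).
- In trials where the active arm started more than 0.4 SD higher (mean imbalance about 0.64 SD), the change score averaged 0.47, 0.61, 0.67 and 0.74 at the four values of rho. ANCOVA stayed at 0.80.

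**Step 5: post value or change as outcome.** If Post = a + t x Arm + b x Pre + error, then Post - Pre = a + t x Arm + (b - 1) x Pre + the same error. The arm effect t and its standard error are identical, which a numerical fit confirmed.

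**The case against.** The strongest reply is that the protocol has chosen no model. To compare changes says what is contrasted, not how, and change analysed with baseline as covariate fits the words (step 5). Covariates are commonly left to the SAP, which may already provide for this. That stands: the protocol contains no error here and omits nothing it had to contain. What remains is that the only statement of the between-arm comparison names change alone and, read plainly, permits the unadjusted test.

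A reader might infer more than the documents support:
- *That the protocol commits to a raw change-score test.* It names no test.
- *That a change-score comparison would be biased.* Under randomization it is unbiased and holds its type I error. The error exists only conditional on the imbalance that occurred.
- *That adjustment is always more precise.* At 10 per arm the advantage is gone from rho about 0.88. Both measurements fall within one visit around a 30-minute session, and QST is averaged over 5 trials, so a high correlation is plausible.
- *That every outcome has a baseline.* Safety and feasibility, the primary outcome, has none.
- *That the floor of the 0-10 scale makes matters worse.* The calculation used unbounded normal data and does not show this. A floor would also strain ANCOVA's straight-line model.
- *That the planned before-after comparison should be reduced to description.* Nothing here requires that.

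**Conclusion.** The point holds as a recommendation of low severity. Aim 2 leaves room for an unadjusted change-score comparison of the secondary pain outcomes although the baseline needed for adjustment is already collected. Adjustment protects against conditional error from chance imbalance: a one-SD imbalance (0.447 outcome SD) shifts the change-score estimate by 0.22 SD at rho 0.5 and 0.09 SD at rho 0.8. It cuts variance by about 20% at rho 0.5, 10% at 0.7 and 4% at 0.8, and raises it by about 1% at 0.9 and 4% at 0.95.

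These sizes rest on 10 per arm, equal pre and post SD, normal outcomes and a correlation that the protocol does not give. The direction of the conditional error is firm for any rho below 1 under equal SDs; the precision gain is not. No stated figure is wrong, and the primary outcome is not affected.

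**What to change.** Add one sentence to Aim 2, and carry it into the SAP: for the 0-10 rating and each QST threshold, the active-minus-sham difference will be estimated by ANCOVA with that measure's own pre-stimulation value as covariate, and reported with a 95% confidence interval. The outcome may be the post-stimulation value or the change, since the treatment estimate is the same. The planned pre-post summaries can stay.

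The cost is one sentence and one degree of freedom (18 to 17), with no new data. If the correlation turns out to be 0.9 to 0.95, the variance is about 1% to 4% higher than that of the raw change score.

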2.0 Background

Pain is a common symptom after a stroke. Up to 50% of stroke survivors experience pain, including muscle and joint pain such as spasticity and shoulder pain, complex regional pain syndrome, and central post-stroke pain (Naess et al., 2012, Harrison and Field, 2015). Pharmacological approaches are currently the mainstream first-line treatment for poststroke pain; however, many recommended medications such as antidepressants or anticonvulsants have limited effectiveness in reducing severe pain (Kumar et al., 2009, Treister et al., 2017). A considerable proportion of poststroke pain symptoms become treatment resistant, which then necessitates the employment of opioids, also known for a high risk of dependency (Kim, 2014, Scuteri et al., 2020).

Emerging evidence indicated that neurostimulation therapy approaches, such as deep brain stimulation (DBS) and vagus nerve stimulation (VNS), could be promising alternatives for the pain treatment of refractory patients and have successfully demonstrated analgesic effects in acute pain, post-surgical pain, and chronic pain disorders (Dang et al., 2019, Bittar et al., 2005, Lempka et al., 2017, Boon et al., 1999, Chakravarthy et al., 2015, Bao et al., 2020). However, these brain stimulation methods are significantly limited due to their costly and invasive nature. Thus, developing non-invasive and affordable neuromodulation methods for the treatment of post-stroke pain will be of great benefit.

Recent innovations in VNS have enabled non-invasive administration at the ear, known as transcutaneous auricular vagus nerve stimulation (taVNS), which has become popular due to minimal side effects and low cost. Importantly, taVNS may produce analgesia and reduce opioid withdrawal by facilitating the release of endogenous opioids via activation of afferent subcortical cranial nerve networks, which subsequently modulate afferent cortical vagal networks controlling pain. However, only limited knowledge currently we have for the feasibility and efficacy of taVNS analgesia in post-stroke pain.

